2.4 Treatments (study treatment, rescue medication, concomitant therapies, compliance)

2.4.1 Study treatment / compliance

Analyses detailed in this section will be performed for Cut-off 1 analysis, Cut-off 2 and final analysis.

For the core part and the extension part, duration of exposure to study drug is defined as (last dose date) – (first dose date) + 31 – sum[(j+1)-th injection date – j-th injection date - 31], where j and j+1 refer to consecutive injections with injection dates more than 31 days apart (as patients are scheduled to take the subcutaneous injections every 28+/- 3 days).

Duration of exposure to study drug of core part and extension part will be summarized by treatment with number and percentage of patients and by duration category (i.e., >= 1 week, >= 2 weeks, >= 3 weeks, >= 4 weeks, >= 8 weeks, >= 12 weeks, >= 24 weeks, >= 36 weeks, >= 48 weeks, >= 60 weeks, >= 72 weeks, until end of the study). The number of patient years of exposure is calculated as (the sum of the number of days of exposure for all

patients in the group)/365.25 and will be summarized for each treatment arm, and by stratification factor Japan vs non-Japan.

Time at risk is the censoring time used for estimating exposure adjusted incidence rate of SAEs or AEs in patients who did not experience the event of interest. For patients who have experienced the event of interest, the actual date of the SAE, or AE onset will be used. Time at risk corresponds to the time window used for adverse event reporting and can serve as a denominator to certain safety analyses (e.g. in exposure-adjusted incidence rates).

Table 2-10 includes definition of time at risk for AE and SAE for Cut-off 1 analysis. It will determine the “end date of the Core part” when all randomized patients completed their assessment during the Core part.

Table 2-10 Time at risk for AE and SAE: Cut-off 1 analysis

Category	For those who completed Week 24 visit	For those discontinued the study prior to Week 24 visit
Time at risk for AE	Number of days in the study from first date of study drug to Week 24 visit date	Number of days in the study from first date of study drug to the earlier date of the following: - Safety cut-off - “End date of the Core part”*
Time at risk for SAE		Number of days in the study from first date of study drug to “end date of the Core part”

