*: “End date of the Core part” will denote the date when all randomized patients complete Week 24 visit or discontinue study drug prior to Week 24 visit. This date is going to be declared by the study team, but not derived from any data.

Table 2-11 includes definition of time at risk for AE and SAE for Cut-off 2 and final analysis. It will determine the “date of Cut-off 2” when all patients entering the Extension part completed their assessment up to Week 48, or EOS visit following premature study drug discontinuation.

Table 2-11 Time at risk for AE and SAE: Cut-off 2 and final analysis

Category	Definition for Cut-off 2 analysis	Definition for final analysis
Time at risk for AE	Number of days in the study from first date of ofatumumab treatment to the earlier date of the following: - Safety cut-off - "Date of Cut-off 2"*	Number of days in the study from first date of ofatumumab treatment to safety cut-off.
Time at risk for SAE	Number of days in the study from first date of ofatumumab treatment to "date of Cut-off 2"*	Number of days in the study from first date of ofatumumab treatment to the last visit date, including Safety FU period.

*: "Date of Cut-off 2" is defined in section 2.1.1

Time-at-risk for AE and time at risk for SAE will be summarized in a similar way to exposure to investigational study medication.

Compliance to the study drug administration schedule will be calculated as duration of exposure to study drug in (days)/duration of on-treatment period in (days) * 100%. This rule means that compliance will be measured during the time interval the patient took study medication: premature discontinuation from study drug will not be considered non-compliance. Compliance to study drug administration will be summarized descriptively on SAF by treatment group. In addition, compliance will be summarized with cumulative number and percentage of patients in each compliance category (i.e., >= 20%, >= 30%, >= 40%, >= 50%, >= 60%, >= 70%, >= 80%, >= 90%, >= 95%, >= 98%, = 100%)

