2.8.1 Adverse events (AEs)

Treatment emergent adverse events (TEAE) is defined as any adverse event which start on or after the day of the first dose of study drug.

TEAEs will be reported if their onset days are no greater than “time at risk for AE”. Similarly, serious TEAEs will be reported if their onset days are no greater than “time at risk for SAE”.

TEAE will be coded by primary system organ class and preferred term according to the Medical Dictionary for Regulatory Activities (MedDRA). The MedDRA version used for reporting the study will be described in a footnote.

Incidence of TEAEs will be summarized (number and percentage of patients reporting any TEAE by primary SOC, preferred term, and treatment group. Serious TEAEs, drug related TEAEs, TEAEs leading to premature discontinuation from study drug, TEAE leading to study drug interruption, and most common TEAEs ($\geq 5\%$ in any of the treatment groups) will be presented in a similar format as adverse events. In addition, incidence of TEAEs will be summarized by SOC, preferred term, and maximum CTCAE grade. Missing CTCAE grade will not be imputed. The CTCAE version 5.0 will be used.

For Cut-off 1 analysis, odds ratios (investigational drug vs. control) with 95% confidence intervals will be presented along with the summary of any TEAEs and the summary of serious TEAEs. Details in calculations of odds ratios and their 95% confidence intervals are provided in Section 5.7.1. Incidence of any TEAEs will be plotted by SOC, along with the odds ratio (and corresponding 95% confidence interval) for TEAEs in each SOC. Odds ratios provide appropriate inferences for events that are likely to occur at certain times (e.g., injection related reactions) while no constant risk over time is expected.

If a patient reports more than one adverse event within the same primary SOC, the patient will be counted only once with the maximum CTCAE grade at the SOC level, where applicable.

All AEs will be presented in listings.

The following summaries will be repeated for Cut-off 2 and final analysis:

- Overall TEAE
- TEAE by CTCAE grade
- Serious TEAE
- Drug-related TEAE
- TEAE causing study drug discontinuation
- TEAE leading to study drug interruption
- Serious TEAE causing study drug discontinuation
- Most common TEAE
- Infections and infestations TEAE

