5.7.2 Exposure adjusted incidence rate and 95% confidence interval

It will be assumed that for each of n patients in a clinical trial the time t_j ($j=1, \dots, n$) to the first incidence of a certain event is observed, or if the event was not experienced, the time is censored at the end of the observation period. The sequence of first occurrences of an event will be modeled to follow approximately a Poisson process θ with constant intensity λ . The rate parameter λ will be estimated by $\hat{\lambda} = \frac{D}{T}$, where $T = \sum_{j=1}^n t_j$ and D is the number of patients with at least one event. Conditionally on T , an exact 95% confidence interval for a Poisson variable with parameter θT and observed value D can be obtained based on (Garwood, 1936), from which an exact 95% confidence interval for $\hat{\lambda} = \frac{D}{T}$ will be derived as follows (Sahai, 1993; Ulm, 1990):

Lower confidence limit $L = \frac{0.5c_{\alpha/2, 2D}}{T}$ for $D > 0$, 0 otherwise,

Upper confidence limit $U = \frac{0.5c_{1-\alpha/2, 2D+2}}{T}$

where $c_{\alpha, k}$ is the α^{th} quantile of the Chi-square distribution with k degrees of freedom.

The SAS procedure GENMOD will be used to fit a Poisson regression model with only treatment as factor, the log-link and natural logarithm of time as the offset variable. The incidence rate (and 95% confidence intervals) are obtained as the exponentiated estimates by treatment (e.g. obtained by statement LSMEANS with option EXP). The data set will include a patient level response variable indicating whether the patient experienced at least one event of a specific type (1=yes, 0=no) and a patient level time variable which is derived as follows:

- For patients who had at least one event of that type: time is calculated as (start day of the first event - date of first administration of study drug+1).
- For patients who did not have an event of that type: time at risk as defined in Section 2.4.1 will be used.

The time will be divided by 365.25 before taking the logarithm transformation as offset variable so that the estimated incidence rate corresponds to an annualized rate.

6 Reference

Cockcroft DW, Gault MJ (1976) Prediction of creatinine clearance from serum creatinine. *Nephron*; 16:31-41

Garwood F. (1936) Fiducial Limits for the Poisson Distribution. *Biometrika* 28, 437-442.

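### At Cut-off 1 the SAE window ends at Week 24 for completers but at a declared study-wide date for discontinuers, so the crude odds ratio compares unequal windows if discontinuation differs by arm

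*SAP*

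**What the plan says.** SAP 2.4.1, Table 2-10, defines time at risk for the Cut-off 1 analysis. For patients who complete Week 24 it is "Number of days in the study from first date of study drug to Week 24 visit date". That text stands in the AE row. The SAE cell for completers is blank in the extracted table, and I read it as merged with the cell above. For patients who discontinue before Week 24, the SAE entry is "Number of days in the study from first date of study drug to “end date of the Core part". The footnote says that this date "will denote the date when all randomized patients complete Week 24 visit or discontinue study drug prior to Week 24 visit", and adds: "This date is going to be declared by the study team, but not derived from any data".

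The definition feeds two kinds of output:

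- SAP 2.8.1 uses it as the counting rule: "serious TEAEs will be reported if their onset days are no greater than “time at risk for SAE". In the same section, Cut-off 1 odds ratios with confidence intervals "will be presented along with the summary of any TEAEs and the summary of serious TEAEs". SAP 5.7.1 shows that these come from a two-by-two table of patients with and without an event.
- SAP 5.7.2 uses it as person-time in exposure-adjusted rates. For patients without the event, "time at risk as defined in Section 2.4.1 will be used".

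Two other places set different limits. SAP 2.8 gives a general Cut-off 1 rule for patients in Safety Follow-up: report up to the earliest of the safety cut-off, the latest visit and the Week 24 visit, unless the text says otherwise. Table 2-11 ends SAE time at risk for the final analysis at the last visit, including Safety Follow-up.

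**The concern.** A completer's window has a fixed length. A discontinuer's window depends on when the last patient was randomized, which has nothing to do with that discontinuer. Because the window also decides which serious events are counted, a discontinuer has more calendar time in which to contribute an SAE, and a crude odds ratio cannot allow for that.

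The difference between completers and discontinuers becomes a difference between arms only if discontinuation, or its calendar timing, differs by arm. The protocol leaves room for this. Sections 3.4 and 3.6 allow patients to stop and switch therapy, including after a relapse. Section 15.4 provides for stopping on confirmed low immunoglobulin. The documents do not say which arm would lose more patients.

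A second point is person-time. With no explicit cap at last contact, days after a patient has withdrawn or been lost could enter the exposure-adjusted denominator. At stake is the clarity of the only placebo-controlled SAE comparison in a study that supports registration.

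**Working it through.** The documents give no figure for these windows, so there is nothing to reproduce. The check is date arithmetic, followed by the expected odds ratio under no treatment effect.

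**Inputs from the documents**
- Week 24 target: Day 168 (SAP Table 2-1).
- 60 patients randomized 2:1, so 40 and 20; 10% dropout, so about 6 (SAP 3).
- Extension of 24 to 48 weeks (protocol 3.1), kept open until the last patient has 24 weeks in it (protocol 3.3).
- Possible visits at Week 84, 96 and beyond (protocol Table 6-1, footnote 20).
- Safety Follow-up of at least 36 weeks = 252 days (protocol 3.1.3).
- Safety cut-off: last dose + 100 days (SAP 2.1.1).

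**Assumptions not in the documents**
- A constant SAE rate, equal in both arms, of 0.05 to 0.20 per patient-year.
- Uniform accrual.
- The split of the six discontinuers between arms.
- Full capture of SAEs.

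**Accrual span.** The first patient has at most 48 weeks of Extension when the last has 24, so the span is at most 48 − 24 = 24 weeks = 168 days. This is inferred; no accrual period is stated.

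**Discontinuer window.** W = 168 + days from the patient's own Week 24 to the end date of the Core part.
- 24-week span: longest 168 + 168 = 336; average 168 + 84 = 252.
- 12-week span: longest 168 + 84 = 252; average 168 + 42 = 210.
- Contingency, with a Week 96 visit for the first patient when the last reaches Week 48 (span 48 weeks = 336 days): longest 168 + 336 = 504; average 168 + 168 = 336.

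**Mean window by arm at W = 252.**
- All six on ofatumumab: (34 × 168 + 6 × 252)/40 = 180.6 against 168.0.
- All six on placebo: 168.0 against (14 × 168 + 6 × 252)/20 = 193.2.
- Four and two (equal 10%): 176.4 in both arms.

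**Expected odds ratio with no true effect.** Risk p(W) = 1 − exp(−rate × W/365.25). At 0.10 per year, p(168) = 0.0450 and p(252) = 0.0667. With all six on placebo, the placebo risk is (14 × 0.0450 + 6 × 0.0667)/20 = 0.0515. The odds ratio is (0.0450/0.9550)/(0.0515/0.9485) = 0.87.

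| Discontinuers, ofatumumab/placebo | W = 252 | W = 336 |
|---|---|---|
| 4/2 | 1.00 | 1.00 |
| 6/0 | 1.08 | 1.15 |
| 2/4 | 0.93 | 0.87 |
| 0/6 | 0.87 | 0.77 |

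The second column applies if every discontinuer has the longest planned window, or the average window under the contingency. The ratios barely move across rates of 0.05 to 0.20.

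**Extra patients with an SAE.** 6 × [p(W) − p(168)] gives 0.07 to 0.25 at 252 days and 0.13 to 0.48 at 336. Over 168 days, 60 × p(168) gives 1.4 to 5.3 patients expected with an SAE.

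**How much of the window is observed.** A patient who stops on Day s is followed to about Day s + 252 at least. The average 252-day window is therefore covered for anyone who stays in follow-up. Day 336 is covered if s ≥ 336 − 252 = 84. Day 504 would need s ≥ 252, so minimum follow-up does not cover it for anyone stopping before Week 24.

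**Non-serious events.** The discontinuer AE window ends at last dose + 100 days, or at the end date of the Core part if earlier. A last dose on Day 28 gives Day 128 and on Day 140 gives Day 240, against 168 for completers. The any-TEAE odds ratio therefore also rests on unequal windows, in either direction.

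**The case against.** The strongest reply is that the long window is deliberate. Protocol 9.5.2.1 includes every serious TEAE and death whatever the safety cut-off, and SAP 1.1 brings discontinuers' Safety Follow-up data into Cut-off 1. Ending completers at Week 24 is also sound, because placebo completers then receive ofatumumab. All of this stands. It justifies a complete SAE table, but it does not require the between-arm odds ratio to use that same window.

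Next, SAP 2.8 may be said to supply the cap already. It yields where something else is explicitly stated, and Table 2-10 is explicit, so the SAP leaves the matter open. Nor would it equalize the windows: a discontinuer with no Week 24 visit is left with the 100-day and latest-visit limits. Similarly, the words about days in the study hint at a cap, but the named end date does not contain one.

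The person-time complaint is narrow. SAP 2.8.1.1 specifies exposure-adjusted rates for the risk search terms, not for the main serious-TEAE table. Their numerator and denominator share one window, so a constant hazard with full capture absorbs its length.

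A reader might infer that discontinuers typically carry a window of more than a year, about three times a completer's, mostly after they have left follow-up. The documents do not support this. A threefold window (504/168) is the maximum under the beyond-Week-72 contingency. Safety Follow-up runs for at least 36 weeks (protocol 3.1.3, Table 6-2), and SAE reporting continues to its last visit (protocol 7.2.2). A reader might also infer bias in a known direction, but at equal dropout the expected odds ratio is 1.00.

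**Conclusion.** The point holds as a minor specification fault. Table 2-10 gives discontinuers a longer SAE window than completers, ends it at a declared date with no explicit cap at last contact, and is not reconciled with SAP 2.8 or aligned with the final-analysis column of Table 2-11.

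The planned inequality is 168 days against up to about 336, average about 252. It reaches the between-arm odds ratio only through unequal discontinuation: 0.87 to 1.08 at 252 days and 0.77 to 1.15 at 336 days, in both cases at the extremes where all six discontinuers are in one arm. Fewer than half an extra patient with an SAE is expected. The result rests on the inferred accrual span, the assumed SAE rates, a constant hazard and the reading of the blank cell as merged. The primary efficacy test is not touched.

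**What to change.** 1. State whether SAP 2.8 or Table 2-10 governs serious events at Cut-off 1. At the same time align the Table 2-10 column header, which refers to leaving the study, with its footnote, which refers to stopping study drug.
2. End discontinuers' SAE time at risk at the earlier of last visit or contact (including Safety Follow-up) and the end date of the Core part, in line with the last-visit limit in the final-analysis column of Table 2-11.
3. Keep the all-SAE table that protocol 9.5.2.1 requires. Base the between-arm odds ratios, for serious and for any TEAE, on a common horizon: the earlier of the patient's actual or planned Week 24 date and last contact. Flag later events in discontinuers. Under a constant hazard, with events captured to that horizon, the expected odds ratio with no effect is then 1.00 for any split of discontinuers.

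Changing only the SAE window would not be enough. A serious event on Day 200 could then count in the any-TEAE odds ratio but not in the serious one.

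The cost is one revised definition and one extra table, and a few late SAEs do not enter the odds ratio. The SAP history places this version after the December 2019 amendment made before database lock. If the Cut-off 1 tables already exist, the common-horizon comparison should be added as a labelled supplementary table.

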9.3 Treatments

Exposure to investigational study medication is defined as the number of days spent on study drug divided by 365.25 days. In this double-blind design all patient will receive injections (active or placebo) to maintain the blind. For the calculation of exposure to study medication the intended dosing frequency will be taken into account and intermediate treatment interruptions will be subtracted when deriving drug exposure.

Exposure to investigational study medication will be summarized by treatment with number and percentage of patients by time category, and with summary statistics of the number of patient years of exposure. Number of patient years will be summarized by age and gender, by gender and weight.

Time-at-risk is defined as the number of days spent in the study, from first dose to the last dose of study medication, plus the safety data cut-off of 100 days. Intermediate treatment interruptions will be included in time-at-risk calculations. Time-at-risk corresponds to the time window used for adverse event reporting and can serve as a denominator to safety (e.g. in exposure-adjusted incidence rates). Time-at-risk will be summarized in a similar way to exposure to investigational study medication.

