On-treatment period is defined as the one between the first date of study drug and 30 days after the last date of study drug. The on-treatment definition applies to efficacy analyses only.

“Safety cut-off” is defined as 100 days after the last dosing date of the study drug.

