2.8 Safety analyses

Safety analyses during the study will be detailed below. All safety analyses will be based on the SAF for Cut-off 1 analysis and ESAF for Cut-off 2 and final analysis, unless explicitly stated otherwise.

Patients will be grouped by the actual treatment received. Safety data for the core part will be reported for the first time when the double-blind loading dose period has been completed by the last patient (Cut-off 1 analysis). Safety data for the extension part including Safety FU period

data will be reported for the first time when the last patient has finished 48 weeks of treatment (Cut-off 2 analysis). Safety data beyond the cut-off 2 will be reported separately.

Unless explicitly otherwise stated, for patients who entered Safety FU period, safety data will be reported up to and including the safety cut-off.

- For Cut-off 1 analysis, safety data reported up to safety cut-off, the latest visit date including Safety FU, or Week 24 visit date, whichever comes first.
- For Cut-off 2 and final analysis, safety data reported up to safety cut-off or the latest visit date including Safety FU, whichever comes first.

The assessment of safety will be primarily based on the frequency of adverse events (including death and non-fatal serious adverse events). Additional safety assessments include laboratory tests, physical examination (including examination of skin), vital sign measures, ECG evaluations and assessment of suicidality. Clinically significant findings in these additional safety assessments will be reported as adverse events and analyzed as such. In addition, all safety assessments will be summarized or listed as appropriate.

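### The final-analysis AE time at risk in SAP Table 2-11 has no stop at the last visit, so patients who move to the umbrella study contribute days on which their AEs are not observed

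*SAP*

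**What the plan says.** SAP 2.4.1, Table 2-11, gives the final-analysis AE time at risk as days in the study from the first date of ofatumumab "treatment to safety cut-off". SAP 2.1.1 says the safety cut-off "is defined as 100 days after the last dosing date of the study drug". The SAE cell beside it ends differently, running from the first date of ofatumumab "treatment to the last visit date, including Safety FU period". The Cut-off 2 AE cell also has a second limit: it takes the earlier of the safety cut-off and the date of Cut-off 2.

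SAP 2.4.1 explains what the quantity is for: "Time at risk is the censoring time used for estimating exposure adjusted incidence rate of SAEs or AEs in patients who did not experience" an AE of the type being counted. SAP 5.7.2 puts it in the denominator: "For patients who did not have an event of that type: time at risk as defined in Section 2.4.1 will be used". The same section describes the model as censoring event-free patients when their observation ends.

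On reporting, SAP 2.8 states: "For Cut-off 2 and final analysis, safety data reported up to safety cut-off or the latest visit date including Safety FU, whichever comes first". SAP 2.4.1 requires time at risk for AEs to be summarised at all three analyses, including the final one.

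**The concern.** Extension completers are offered transfer to the umbrella study (SAP 1.1). Only completers who decline it, and patients who stop treatment early, enter Safety Follow-up. Protocol 7.1 collects AEs to the end of study participation. For a transferring patient that is the EOS visit, normally well short of 100 days after the last dose.

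The final-analysis AE cell makes no allowance for this. An event-free transferring patient is credited with time after EOS in which an AE could not have been recorded here. That inflates person-time without any chance of adding events, so a rate computed from it is biased downward. The bias is proportionally larger for patients with less ofatumumab time, which here means those who switched from placebo at Week 24.

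**Working it through.** The documents give no time-at-risk total or exposure-adjusted rate to reproduce. The check compares the cell as written with the same cell capped at the last visit.

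**Inputs from the documents**
- Safety cut-off: last dose + 100 days (SAP 2.1.1).
- Extension of 24 to 48 weeks (SAP 1.1). Ofatumumab time to EOS is therefore 24 to 48 weeks for placebo switchers and 48 to 72 weeks for patients on ofatumumab throughout.
- Dosing every 4 weeks, ±3 days (Protocol 5.5.4).
- 60 patients randomised 2:1, so 40 and 20 planned.

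**Assumptions (not in the documents)**
- Gap from last dose to EOS: 28 days, range 0 to 31.
- Share *s* of completers who transfer: 1 or 0.5.
- Constant event rate *L*: 0.01 (rare) or 1 per year.

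**Step 1: unobserved days per event-free transferring patient.** *x* = 100 − gap. A gap of 28 gives 72; 31 gives 69; 0 gives 100.

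**Step 2: denominator per such patient.** The observed window is τ = 7 × weeks + 1 days; the cell as written gives τ + 72.

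| Weeks on ofatumumab | Observed days | Days as written |
|---|---|---|
| 24 | 169 | 241 |
| 48 | 337 | 409 |
| 72 | 505 | 577 |

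**Step 3: effect on a rate D/T (SAP 5.7.2).** Per patient, expected events are 1 − exp(−Lτ) and expected observed time is (1 − exp(−Lτ))/L. The cell as written adds s·x·exp(−Lτ). With τ and x in years:

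ratio (as written / capped) = 1 / [1 + s·x·L·exp(−Lτ) / (1 − exp(−Lτ))]

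For rare events this tends to τ/(τ + s·x); for example 169/241 = 0.70.

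| Case | 24 wk | 48 wk | 72 wk |
|---|---|---|---|
| Gap 28, s = 1, L = 0.01 | 0.702 | 0.825 | 0.876 |
| Gap 28, s = 1, L = 1 | 0.749 | 0.885 | 0.938 |
| Gap 28, s = 0.5, L = 0.01 | 0.825 | 0.904 | 0.934 |
| Gap 0, s = 1, L = 0.01 | 0.629 | 0.772 | 0.836 |
| Gap 31, s = 1, L = 0.01 | 0.711 | 0.831 | 0.881 |

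One minus each entry is the understatement. The half-transfer row credits non-transferring patients with τ only. If they are credited with the full 100 days they are actually followed, the 24-week entry becomes ((169 + 241)/2)/241 = 205/241 = 0.85, a slightly smaller effect.

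**Step 4: the time-at-risk summary.** With planned numbers, everyone event-free and everyone transferring:
- 40 patients at 48 weeks: 40 × 337/365.25 = 36.9 patient-years observed; 40 × 409/365.25 = 44.8 as written.
- 20 switchers at 24 weeks: 20 × 169/365.25 = 9.3 observed; 20 × 241/365.25 = 13.2 as written.

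**The case against.** **The cell speaks of days in the study, and a patient who has transferred is no longer in it.** This reading is possible, and SAP 5.7.2's statement about when observation ends favours it. But the Cut-off 2 AE cell opens with the same words and still adds an explicit second limit. Protocol 9.3 also begins from days spent in the study, then counts "from first dose to the last dose of study medication, plus the safety data cut-off of 100 days". The words alone do not supply the cap.

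**Numerator and denominator share one window.** SAP 2.8.1 reports TEAEs only when onset falls within the AE time at risk, and the SAP 2.8 limit quoted above is introduced for patients who entered Safety Follow-up. Both points stand. A reader might infer that the SAP writes down two conflicting windows for transferring patients; it does not. The fault is that the single written window extends past the data: no AEs are collected here after EOS, whatever the rule admits.

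**The affected rate may not be produced.** This largely stands. The summaries that SAP 2.8.1 repeats for the final analysis are incidence tables. SAP 2.8.1.1 plans exposure-adjusted rates for AEs of special interest without clearly assigning them to the final analysis. What is certainly affected is the time-at-risk summary.

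**A distorted comparison between the two displayed groups.** A reader might infer this, because switchers are diluted more (at 24 against 48 weeks, 0.702/0.825 = 0.85). The documents do not support it as a finding: odds ratios and rate ratios are specified for Cut-off 1 only, and no final-analysis rate contrast is planned.

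**Conclusion.** Wrong as written, and minor. The final-analysis AE cell credits each event-free transferring patient with about 72 unobserved days (69 to 100 for gaps of 31 to 0 days). This is at odds with the censoring principle in SAP 5.7.2 and with the neighbouring SAE cell. It overstates the required time-at-risk summary and would understate any exposure-adjusted AE rate produced at that analysis.

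If all completers transfer, the understatement at 24, 48 and 72 weeks on ofatumumab is about 30%, 18% and 12% for rare events, and about 25%, 12% and 6% at 1 event per year. If half transfer, it is at most about 18%, 10% and 7% for rare events. A reader might take 30% as the general size; it applies only to rare events, full transfer and switchers with the minimum 24-week extension.

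The gap, transfer share and event rates are assumptions. The direction is not, provided some event-free patients transfer and their gap is under 100 days. Crude incidence, the Cut-off 1 ratios and patients followed through Safety Follow-up do not change.

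**What to change.** In SAP Table 2-11, final-analysis column, AE row, end the period at *the earlier of the safety cut-off and the last visit date including Safety FU*. This changes one cell and needs no new data. The time-at-risk summary becomes shorter, and any final exposure-adjusted AE rate rises: by 1/0.702 = 1.42 times in the largest 28-day-gap case above, and by 1/0.938 = 1.07 times in the smallest of the full-transfer cases. It would also help to state in SAP 2.8.1.1 whether exposure-adjusted rates will be produced at the final analysis.
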